8.12. Questionnaires

Patient Health Questionnaire (PHQ-9) and Generalised Anxiety Disorder (GAD-7) Questionnaire

PHQ-9 and GAD questionnaires will be used at the discretion of the Investigator to assess participants' eligibility in terms of ability to tolerate isolation in the quarantine unit.

8.13. Nasal Discharge Collection from Paper Tissues

Each participant will be given pre-weighed packets of paper tissues. Participants will be asked to place single tissues used for nose blowing or sneezing into a specified bag (for that participant only).

A daily 24-hour collection will take place throughout the quarantine period. Distribution of paper tissues and bags will start on Day -1, with the first collection on Day 0. Thereafter distribution and collection of tissues will occur at 08:00h (\pm 1 hour). Tissues will be handed out daily and collection will occur until the discharge from quarantine.

In the event of a participant staying in quarantine beyond the planned day of discharge, the 24-hour distribution and collection of tissues and bags will continue until the participant is finally discharged from quarantine.

24-hour paper tissue collections will be analysed to determine the following over the quarantine period:

- 24-hour nasal discharge weight.
- The number of paper tissue used for nasal discharge over 24-hour period.

8.14. Urine Samples and Assessments

8.14.1. Urinalysis

Clinical urine safety analysis will be undertaken using commercially available urine test strips that provide an instant result that will be documented in the source data.

hVIVO template identifier: (G_0687) v3.0

Urinalysis will be performed to evaluate the parameters described in [Appendix 10.2](#).

If the dipstick yields abnormal results, a urine sample may be sent for microscopy, culture and sensitivity (MCS), at the Investigator's discretion. MCS will include but is not limited to RBC, WBC, epithelial cells, crystals, casts, and bacteria.

Urine safety analysis values will be evaluated by the Investigator for clinical relevance. Those deemed to be clinically significant will be reported as AEs.

8.14.2. Drugs of Abuse and Cotinine

Urinalysis will be performed for drugs of abuse and cotinine using commercially available kits that provide an instant result, which will be documented in the source data.

Drugs of abuse screen will include (but is not limited to) amphetamines, barbiturates, cocaine, opiates, cannabinoids and benzodiazepines.

8.14.3. Pregnancy Test

Female participants of childbearing potential are to have a urine pregnancy test at screening. Participants will only be enrolled if the pregnancy test is negative.

Note: Pregnancy test must be performed even if the participant is menstruating at the time of the study visit.

All female participants will have a serum sample tested for β -human chorionic gonadotrophin (β -hCG) on admission to quarantine.

Blood samples will be tested for serum FSH in post-menopausal women only.

8.15. Blood Samples

A maximum volume of 550 mL of blood may be taken from each participant from screening through to the final study contact. If additional samples are required in excess of this amount, e.g., to monitor abnormalities, these will be collected at the discretion of the Investigator.

8.15.1. Safety Blood Analysis and Assessments

[Appendix 10.2](#) describes the safety blood tests that will be performed including, but not limited to, haematology, biochemistry, thyroid function test and cardiac enzymes. Additional safety assessments (e.g. coagulation) will be conducted at the discretion of the PI/Investigator, as required.

Serum samples will be tested for serum follicle stimulating hormone (FSH) in post-menopausal women only.

8.15.2. Challenge Virus Serology Samples

A participant must be sero-suitable to take part in the study; i.e. he/she must have low pre-existing serum levels of antibodies specific to the Challenge Virus. This antibody titer cut-off for serosuitability will be described in the AP.

8.15.3. Blood for Immunology Biomarker Evaluations

Blood will be taken for analysis related to the study exploratory endpoints. Immunology analysis will be performed in relation to the vaccine as well as viral infection and susceptibility, and may include, but not limited to:

- Serum for:
 - Humoral immune response (e.g. serum PreF and PostF IgG, IgA, sIgA, MNA)
 - Innate cytokines and chemokines response
 - Non-vaccine antigen-binding antibody assay for serological detection/seroconversion of community acquired RSV infection between vaccination and viral challenge.
- Whole blood for:
 - Genomics (e.g. HLA typing, SNPs, GWAS)
 - Transcriptomics (e.g. RNA-Seq, single cell RNA-Seq)
 - Cell mediated immunity (e.g. IFN γ T cell ELISPOT)
 - Cellular markers (e.g. Flow cytometry ICS, cytokine secretion from peptide stimulated PBMCs)

The detailed description of the assays performed in the study will be documented in the AP as appropriate.

8.16. Nasal Samples

The following upper respiratory sampling will be performed:

- Nasal sample (Nasopharyngeal swab or nasal wash) will be performed to collect samples of nasal cells and epithelial lining fluid for:
 - Respiratory Pathogen Screen
 - RSV discharge test
 - RSV quantification
 - Antibody binding and neutralisation assays
 - Exploratory purposes (remaining cells and epithelial lining fluid from the nasal samples may be stored for exploratory purposes).
 - Tolerance of the procedure may be determined at the screening visit.
- Nasosorption (Nasal wick) may be performed to collect epithelial lining fluid for assays such as:
 - Antibody binding and neutralisation assays
 - Proteomics (e.g. cytokines and chemokines)
 - RSV quantification
 - Transcriptomics
 - Exploratory purposes (remaining epithelial lining fluid may be stored for exploratory purposes).

8.16.1. Respiratory Pathogen Screen

On entry to quarantine, nasal samples will be collected and screened for the presence of respiratory pathogens, including SARS-CoV-2 virus, by multiplexed PCR-based methodology. A positive result from this pathogen screen could potentially contraindicate a participant's participation in the study. The methodology to be used to conduct the respiratory virus screen will be documented in the AP. Additional

test may be conducted if the results from the first test are invalid to support study eligibility prior to virus inoculation, or if a community acquired infection is suspected during quarantine.

A nasal sample might also be collected prior to vaccination on Day -28 to determine the presence of the SARS-CoV-2 virus.

Any additional screening tests will be conducted at the discretion of the PI.

8.16.2. Rapid Viral Antigen Test

A rapid diagnostic test (e.g. RVAT) will be used to determine the presence of RSV in a nasal sample taken prior to discharge from the Quarantine Unit on Day 12. (and subsequent days if, at the discretion of the PI, an extended quarantine stay is required due to test result and/or the presence of clinical symptoms) A PCR screening test may be used as an alternative test for this purpose.

8.16.3. Viral Load

Viral load will be determined by quantitative reverse transcription polymerase chain reaction (qRT-PCR) and viral culture assays to investigate the following parameters:

- viral dynamics (e.g. AUC, duration, peak, time to peak)
- infectivity status and rate
- symptomatic infectivity status and rate

8.16.4. Biomarkers

The nasal sample and/or nasal wick (Class 1 Device) procedure may be used to collect samples of epithelial lining fluid (ELF) for:

- Antibody binding and neutralisation assays
- Proteomics (e.g. cytokines and chemokines)
- RSV quantification
- Transcriptomics
- Exploratory purposes (remaining epithelial lining fluid may be stored for exploratory purposes).

8.17. Recording of Adverse Events and Serious Adverse Events

The PI/Investigator is responsible for ensuring that all AEs, SAEs and pregnancies are identified, evaluated, recorded and reported in a timely manner as per Regulatory requirements and hVIVO's SOPs, and also for ensuring that the medical management (including follow up) of AEs, SAEs and, where appropriate, pregnancy symptoms/complications is provided by competent Investigator Site staff.

The Sponsor of the study will also perform an evaluation of seriousness, causality and expectedness of all SAEs.

The definitions of an AE or SAE, as well as the method of recording, evaluating, and assessing causality of AE and SAE and the procedures for completing and transmitting AE, SAE, and other reportable safety event reports can be found in [Appendix 10.3](#).

8.17.1. Time Period and Frequency for Collecting AE and SAE Information

All AEs/SAEs will be collected from the signing of the ICF until the last Follow-up Visit at the time points specified in the SoA ([Section 1.3](#)).

Investigators are not obligated to actively seek AE or SAE after conclusion of the study participation. However, if the investigator learns of any SAE, including a death, at any time after a participant has been discharged from the study, and he/she considers the event to be reasonably related to the study intervention or study participation, the investigator must promptly notify the sponsor.

8.17.2. Method of Detecting AEs and SAEs

The method of recording, evaluating, and assessing causality of AE and SAE and the procedures for completing and transmitting SAE reports are provided in [Appendix 10.3](#).

Care will be taken not to introduce bias when detecting AEs and/or SAEs. Open-ended and non-leading verbal questioning of the participant is the preferred method to inquire about AE occurrences.

8.17.2.1. Solicited AEs

Solicited AEs are pre-defined events for which participants are specifically questioned and which are noted by participants in their diaries ([Section 8.11.1](#)). Information related to solicited events as defined in [Appendix 10.3](#) will be recorded by participants in a diary after vaccination. Each participant will be provided with a diary and instructions on how to complete the diary. There will be a minimum 30-minute post vaccination assessment of solicited events by the Investigator. The participant diary information will be transcribed by the study personnel in the appropriate eCRF pages. Participants will be asked to take a daily temperature measurement and to note in the diary occurrences of symptoms beginning on the evening of the study vaccine dosing day (on Study Day -28) and daily for the total of 7 days post-vaccination. Local reactions reported via the VDC are redness, swelling, and pain at the injection site. Systemic events reported via the VDC are fever, fatigue, headache, vomiting, nausea, diarrhea, muscle pain, and joint pain.

For all ongoing systemic events 7 days post vaccination, the stop date will be recorded in the CRF.

8.17.2.2. Unsolicited AEs

Unsolicited AEs are all AEs for which participants are not specifically questioned in the participant diary. Unsolicited AEs monitoring will begin after vaccination on the Vaccination (Study Day -28) Visit and will continue through 30 days post vaccination. Any unsolicited AEs that occurs after 30 days post-vaccination through to study completion will be recorded by the Investigator and included in the study database. Adverse events will be followed by the Investigator as specified in [Section 8.17.3](#).

8.17.2.3. Medically Attended AEs

A medically attended adverse event (MAE) is an adverse event, whether considered related to the investigational vaccine or not, that led to the participant seeking evaluation by a healthcare provider. MAEs will be assessed between study day -28 and study Day +155 (6 months post-vaccination follow up), through self-report by participant and by query by the Investigator/designee at study visits and in any protocol specified telephone outreach.

8.17.3. Follow-up of AEs and SAEs

After the initial AE/SAE report, the investigator is required to proactively follow each participant at subsequent visits/contacts. All AEs/SAEs, will be followed until resolution, stabilisation, the event is otherwise explained, or the participant is lost to follow-up (as defined in [Section 7.3](#)). Further information on follow-up procedures is provided in [Appendix 10.3](#).

8.17.4. Regulatory Reporting Requirements for SAEs

Prompt notification by the investigator to the sponsor of a SAE is essential so that legal obligations and ethical responsibilities towards the safety of participants and the safety of a study intervention under clinical investigation are met.

The following reporting process will be followed:

- PI will send SAE/pregnancy forms to the Sponsor's PV within 24 hours of becoming aware of the event
- Sponsor's PV will assess expectedness to determine if the SAE requires expedited reporting
- Sponsor's PV will send query to the PI if additional information is needed
- Sponsor's PV will report the case to the Medicines and Healthcare Regulatory Agency (MHRA) via the EudraVigilance Database Management System EVWEB (or alternatively using MHRA eSUSAR tool)
- PI will report SUSAR and other relevant safety information to the Ethics Committee in accordance with REC guidelines.

The Sponsor has a legal responsibility to notify both the local regulatory authority and other regulatory agencies about the safety of a study intervention under clinical investigation. The Sponsor will comply with country-specific regulatory requirements relating to safety reporting to the regulatory authority, Research Ethics Committee (REC) and investigators.

The Sponsor is responsible for assessing SUSARs, unblinding potential SUSARs, and reporting SUSARs to the MHRA and REC. The Sponsor shall ensure that all relevant information about a SUSAR that occurs during the course of a clinical trial in the UK and is fatal or life threatening, is reported as soon as possible to the MHRA and the REC. This needs to be done within 7 calendar days after the Sponsor became aware of the event. Any additional relevant information should be sent within 8 calendar days of the first report being sent.

The Sponsor shall ensure that a SUSAR which is not fatal or life-threatening is reported as soon as possible and in any event within 15 calendar days after the Sponsor became aware of the event.

In accordance with ICH GCP guidelines, the Sponsor will also inform the Investigator of findings that could affect adversely the safety of participants and/or impact the conduct of the trial. Annual safety reporting to the national Competent Authority (MHRA) and the Ethics Committee will be in agreement with ICH guideline E2F “Note for guidance on Development Safety Update Reports (DSUR)” .

In addition, any other safety issue which may alter the current benefit-risk assessment of the IMP will be reported by the Sponsor (or delegate) on an expedited basis to Competent Authorities, Ethics Committees and the Investigator.

The detailed procedure of the SAE/SUSAR reporting will be described in a Pharmacovigilance Management Plan that will be finalised before the start of the study to exactly define the different tasks of the Investigator, Sponsor and Sponsor's Pharmacovigilance vendor.

An investigator who receives an investigator safety report describing a SAE or other specific safety information (e.g., summary or listing of SAEs/SUSARs) from the sponsor will review and will notify the REC, if appropriate according to local requirements.

Further information on regulatory reporting requirements is provided in [Appendix 10.3](#).

8.17.5. Pregnancy

Details of all pregnancies in female participants and, if indicated, female partners of male participants will be collected from study specific informed consent and until the last study assessment as outlined in the SoA. If a pregnancy is reported, the Investigator should inform the sponsor within 24 hours of learning of the pregnancy and should follow the procedures outlined in [Appendix 10.3](#).

Abnormal pregnancy outcomes (e.g., spontaneous abortion, foetal death, stillbirth, congenital anomalies, ectopic pregnancy) are considered SAEs.

8.18. Treatment of Overdose

For this study, any dose of any drug administered as part of the study greater than the dose prescribed by the protocol will be considered an overdose.

In the event of an overdose, the Investigator should:

1. Contact the Medical Monitor immediately.
2. Closely monitor the participant for any AE/SAE and laboratory abnormalities associated with overdose and participants will be clinically followed up until the AE has resolved.
3. Document the quantity of the excess dose as well as the duration of the overdose in the CRF.

The Sponsor is responsible for notifying the MHRA and REC of the potential serious breach within 7 days of becoming aware of it.

8.19. Biomarkers

Biomarkers may be evaluated from blood and nasal samples, as detailed in Section 8.15.3 and 8.16 respectively.

Samples may be used for exploratory biomarker research related to

- immunity and susceptibility to RSV infection
- RSV vaccine responses
- Immune response to RSV infection

8.20. Immunogenicity Assessments

Samples will be taken and assessed for immunological endpoints as detailed in Section 8.15.3 and 8.16 respectively. Samples may also be retained for future usage as described in [Section 10.1.4](#).

9. Statistical Considerations

9.1. Statistical Hypotheses

S-cubed will perform the statistical analysis for the study. Full details of the planned statistical analysis will be presented in the Statistical Analysis Plan (SAP). Any deviations from the SAP will be documented in the Clinical Study Report (CSR).

9.2. Sample Size Determination

The statistical powering selected for this study is estimated to be sufficient for the primary objective and the primary endpoint family. The primary endpoint family consists of 3 endpoints listed below with their associated sample size estimates. As an exploratory proof of concept study, no adjustment for Type I error is planned in regard to the primary endpoint family. The sample size of 62 participants (31 in each group) will allow:

- Detection of a 70% relative reduction in the PCR-AUC virology with RSVpreF assuming a 96%CV in the control arm. The power for this endpoint is for 80% using a two-sided type-I error rate of 5%. The PCR-AUC data is based on log transformed PCR data.
- Detection of a 60% relative reduction in the symptomatic-infection rate with RSVpreF assuming a 59.26% rate in the control group (i.e. a rate of 23.7% in the RSVpreF group). The power for this endpoint is 80% using a two-sided type-I error rate of 5%. Symptomatic-infection is defined as:
 - Lab confirmed infection (two detectable (\geq Lower Limit of Detection LLOD) RT-PCR measurements (reported on 2 or more consecutive days), starting two days post-viral challenge (Day +2) up to discharge from quarantine), and
 - Either one or more positive clinical symptoms of any grade from two different categories in the symptom scoring system (Upper Respiratory, Lower Respiratory, Systemic), or one Grade 2 symptom from any category
- Detection of an 80% relative reduction in the total symptoms with RSVpreF assuming a 113.55% common CV. The power for this endpoint is at least 80% using a one sided type-I error rate of 5%.

The sample sizes indicate the number of vaccinated participants to be inoculated with the challenge virus per treatment group, more will be vaccinated in order to achieve the inoculation numbers. Therefore, up to 72 participants will be enrolled and vaccinated with the study vaccine, with 62 participants challenged with the study virus

9.3. Populations for Analyses

The following populations are defined:

Population	Description
ITTc (Intent-to-Treat-Challenge) Analysis Set	All participants randomly assigned to study intervention and who take a dose of study vaccine / placebo and were given viral challenge.

Per Protocol (PP) Analysis Set	All participants randomly assigned to study intervention and who take a dose of study vaccine / placebo, are given viral challenge, have no major protocol deviations, and who complete quarantine (Day 12).
Safety Analysis Set	All participants randomly assigned to study intervention and who take a dose of study intervention (study vaccine / placebo), regardless of whether they received the challenge virus or not. Participants will be analysed according to the intervention they actually received.

The primary analysis will be on the ITTc Analysis Set. Analysis using the PP Analysis Set will be secondary. The safety evaluation will be performed on the Safety Analysis Set.

Membership of subjects in each analysis set will be determined at a planned blinded data review meeting (BDRM), prior to the any analysis and database lock.

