
 To evaluate the safety and reactogenicity of RSVpreF, when compared to placebo 	
To evaluate the incidence of the following endpoints:
 
 Occurrence of solicited local reactions and systemic events within 7 days (i.e., on the day of vaccination and 6 subsequent days) after vaccination. Occurrence of unsolicited adverse events (AEs) within 30 days (i.e., on the day of vaccination and 29 subsequent days) after vaccination Occurrence of medically attended AEs (MAEs) and serious adverse events (SAEs) from vaccination (Day -28) up to study end (Day +155).

 To evaluate the safety of the RSV challenge model. 	
To list the incidence of the following endpoints:
 
 Occurrence of unsolicited AEs within 30 days post-viral challenge (Day 0) up to Day +28 follow up. Occurrence of SAEs related to the viral challenge from the viral challenge (Day 0) up to Day +28 follow up. Occurrence of haematological and biochemical laboratory abnormalities during the quarantine period. Use of concomitant medications within 30 days post-viral challenge (Day 0 up to Day +28 follow up).
TERTIARY	
Tertiary/exploratory endpoints include but are not limited to the following.	

 To evaluate the effect of baseline immune status on immunogenicity and efficacy of the RSVpreF, when compared to placebo 	
 The primary, secondary, and tertiary endpoints may be explored in relation to the baseline status of participants and the response to vaccination.

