4.1. Overall Design

This is a randomised, Phase 2a, double blind, placebo-controlled study to evaluate the safety, immunogenicity and efficacy of an RSV vaccine against RSV-A Memphis 37b infection in healthy participants.

The total duration of study participation for a participant is approximately 6 months after vaccination, with the following sequence and duration of study periods:

Screening Phase:

- Screening prior to vaccination from Day -84 to Day -29 (Day -118 for RSV serology) Pre-screening data collected through the hVIVO generic screening process prior to signing the study specific consent form, and prior to vaccination from Day -84 to Day -29 (Day -118 for RSV serology) may be transferred to this study after study-specific consent form has been signed by the participant. Pre-screening data obtained prior to this window can be re-assessed any time prior to vaccination from Day -84 to Day -29.

Vaccination Phase:

- Vaccination on Day -28 (± 3 days), participants will be randomised 1:1 to receive RSVpreF or placebo
- Follow up clinic visit 1 day post vaccination
- Follow up clinic visit 7 days post vaccination (± 1 day)

Quarantine Phase:

- Admission to the Quarantine Unit on Day -2/-1; resident in the Quarantine Unit for approximately 15 days, from admission on Day -2 to planned discharge on Day +12.
- Challenge with Challenge Virus on Day 0.
- Discharge from quarantine planned on Day +12

Follow-Up Phase:

- Day +28 (± 3 days).
- Day +155 (± 14 days)

Participants will be pre-screened for susceptibility to RSV infection, i.e., have levels of RSV neutralising antibodies compatible with susceptibility to RSV infection.

Participants will be randomised to receive a single intramuscular dose of RSVpreF or Placebo on Day -28 (± 3 days):

- **Reference article product**
 - PF-06928316 also known as RSVpreF
 - Dose: 120mcg

- **Placebo product**

- Placebo to match vaccine

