7.2. Participant Discontinuation

Participants will be withdrawn from study intervention for the reasons listed below. These participants must not receive any additional intervention but should continue to be followed for safety. Additional unscheduled visits may be performed for safety reasons.

- Non-compliance with the study requirements and restrictions.
- Clinically significant abnormal laboratory findings, which in the opinion of the Investigator(s) and/or Sponsor, precludes further participation in the study.
- Development of inter-current illness which, in the opinion of the Investigator would compromise the health of the participant or the study objectives.
- The Investigator's decision that withdrawal from further participation would be in the participant's best interest.
- Termination of the study at the discretion of the Investigator(s) or Sponsor for safety, behavioural, or administrative reasons.
- The wish of the participant.
- Any intervention related SAEs.
- Anaphylactic reaction following dosing.
- The participant becomes pregnant.

When the target evaluable participant number is achieved, for a given quarantine group or for the overall study, reserve vaccinated participants may not be inoculated with challenge virus. In addition to post vaccination visits (1 and 7 days post vaccination), participants may additionally have assessments performed on Day -2/-1/0 and the final follow up visit Day +155 (± 14 days) for safety and immunogenicity.

Participants who are withdrawn from the study, will be requested to attend an Early Withdrawal Visit, with assessments as detailed in the SoA.

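### Challenge-model safety endpoints are assigned to a set that includes vaccinated participants who were never challenged, so their absolute incidence can be understated by up to 13.9% in relative terms (minor)

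*Combined protocol and SAP*

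**What the plan says.** **Analysis set.** Section 9.3 defines three sets and gives one rule for safety: "The safety evaluation will be performed on the Safety Analysis Set". The Safety Analysis Set holds everyone randomised who received vaccine or placebo, "regardless of whether they received the challenge virus or not", analysed by the intervention actually received. The only sets restricted to challenged participants are the ITTc and Per Protocol sets, and Section 9.3 gives both to the primary and secondary analyses rather than to safety.

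**Endpoints.** Section 3 (repeated in the Section 1.1 synopsis) has two safety objectives. The first concerns RSVpreF against placebo: solicited events, unsolicited AEs to 30 days after vaccination, and MAEs and SAEs from vaccination to Day +155. The second concerns the challenge model. It covers unsolicited AEs and concomitant medication from Day 0 to Day +28, challenge-related SAEs over the same period, and "Occurrence of haematological and biochemical laboratory abnormalities during the quarantine period".

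**Unchallenged participants are planned.** Section 9.2 says: "Therefore, up to 72 participants will be enrolled and vaccinated with the study vaccine, with 62 participants challenged with the study virus". Section 7.2 adds that once the target number is reached, "reserve vaccinated participants may not be inoculated with challenge virus". Section 7.4 allows people vaccinated but not inoculated to be replaced.

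**Reporting.** Section 9.6.8 summarises safety descriptively, with AEs as counts and percentages of participants by treatment group. It names no separate denominator for the challenge phase.

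**The concern.** The second safety objective asks how often something happens after the virus is given. Section 10.6.1 defines Day 0 as the day of challenge, so strictly a participant who is never challenged has no Day 0 and cannot contribute a post-challenge event. Section 7.2 gives uninoculated reserves the post-vaccination visits, possible assessments on Day -2/-1/0 and the final visit. It lists neither quarantine follow-up nor a Day +28 visit for them. Counting them in the denominator adds people who were neither exposed nor observed for these endpoints.

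The error runs in the reassuring direction: reported challenge-phase incidence is too low. What is at stake is the accuracy of one descriptive secondary objective. The primary efficacy result, which uses the ITTc set, is not touched.

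**Working it through.** **Inputs.** All are from the protocol: 31 per group and 62 in total (Section 9.2, "The sample size of 62 participants (31 in each group) will allow"); up to 72 vaccinated and 62 challenged (Section 9.2); 1:1 allocation (Section 4.1).

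**1. The plan's own figures.** For symptomatic infection, Section 9.2 takes 59.26% against 23.7%, two-sided 5%, 80% power. With the pooled-variance formula for two proportions:

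n = [1.96·√(2·0.4148·0.5852) + 0.8416·√(0.5926·0.4074 + 0.237·0.763)]² / (0.5926 − 0.237)² ≈ 28.9, so 29 per group.

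Power at 31 per group is 82.8%, so 31 is consistent with the stated design. The step from 62 to 72 allows for 10/72 = 13.9% not reaching challenge: 62 / (1 − 10/72) = 72.

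**2. Dilution factor.** Let p be the incidence among challenged participants, c the number challenged and v the number vaccinated. On the Safety Analysis Set the reported figure is p·c/v, so the relative understatement is 1 − c/v. This assumes that the full set is the denominator and that no unchallenged person's events are counted.

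| Vaccinated | Challenged | c/v | Relative understatement |
|---|---|---|---|
| 62 | 62 | 1.000 | 0% |
| 66 | 62 | 0.939 | 6.1% |
| 72 | 62 | 0.861 | 13.9% |

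Two assumed departures from those numbers show that 13.9% is the planned maximum and not a strict bound. If only 58 of 72 were challenged, the understatement would be 19.4%. If the ten extra participants allowed by Section 9.7 came on top of 72 and were all challenged, it would be 10/82 = 12.2%.

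**3. Absolute size at 72 and 62.** The shift is p × 10/72.

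| True incidence | Reported | Shift (percentage points) |
|---|---|---|
| 5% | 4.3% | 0.7 |
| 10% | 8.6% | 1.4 |
| 20% | 17.2% | 2.8 |
| 30% | 25.8% | 4.2 |

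In counts, 6 participants with an event are 9.7% of 62 but 8.3% of 72; 12 are 19.4% against 16.7%.

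**4. Between arms.** If the unchallenged are balanced, each arm is scaled by 31/36 = 0.861 and the ratio between arms does not change. They need not be balanced even when 31 are challenged in each arm, because a replacement joins the arm of the person replaced (Section 7.4). As an assumed example, take 31 challenged of 39 vaccinated in one arm and 31 of 33 in the other, again 72 and 62 in total. A true 30% in both would appear as 30% × 31/39 = 23.8% and 30% × 31/33 = 28.2%.

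**The case against.** **The denominators are not yet fixed.** Section 9.3 names an analysis set, and Sections 9.1, 9.4.1 and 9.5 leave detailed presentation to an SAP whose text is not among the documents. That SAP could use participants at risk, or the number with data for laboratory results, and the problem would then not arise. This stands as a limit on certainty. It does not remove the point: Section 9.3 as written covers all safety evaluation, and no other section makes an exception.

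**The challenge objective is descriptive.** Section 3 speaks of listing incidence and, unlike the vaccine-safety objective, does not mention comparison with placebo. No safety test is planned. The stopping rules in Section 7.5 (Table 4) act on individual events, an overall pattern or two affected participants, never on percentages. Section 9.6.1 also reports how many received the virus, so a reader given challenge-phase counts could recompute the rate. All of this stands, and it keeps the point minor.

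**Distortion between arms.** A reader might infer that the treatment comparison after challenge is materially biased, for instance by supposing that 28 were challenged in one arm and 34 in the other. The documents do not support that. Section 9.7 has an unblinded statistician monitor losses between vaccination and inoculation so that inoculated numbers are balanced, with 31 evaluable per group. Unequal numbers of unchallenged people remain possible, as shown in the working, but no formal safety comparison rests on them.

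**Everything after inoculation.** A reader might also conclude that every summary from inoculation onward should be limited to challenged participants. That would damage the vaccine-safety objective. Its MAE and SAE endpoints run to Day +155, its 30-day window for unsolicited AEs can extend past Day 0, and Section 7.2 provides for uninoculated reserves to attend the final visit for safety.

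**Conclusion.** The point holds as a minor error in the choice of denominator. Applied as written, Section 9.3 understates the absolute incidence of the challenge-model safety endpoints by 0% to 13.9% in relative terms under the planned numbers. The 13.9% should not be read as percentage points: the absolute shift is 1.4 points at a true 10% and 4.2 points at a true 30%.

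The conclusion assumes that percentages use the full Safety Analysis Set, and the upper figure that 72 are vaccinated and 62 challenged. Vaccine-safety endpoints are correctly placed on the Safety Analysis Set.

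**What to change.** Add to Section 9.3, and carry into the SAP before it is signed and the data are unblinded, a rule set by endpoint and not by date:

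- The challenge-model safety endpoints in Section 3, including post-inoculation laboratory summaries in quarantine, use as denominator the participants who received the challenge virus, by intervention actually received.
- All vaccine-safety endpoints (solicited events, unsolicited AEs to 30 days after vaccination, MAEs and SAEs to Day +155) stay on the full Safety Analysis Set, including unchallenged participants.

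The first rule needs its own wording because none of the three sets is explicitly both challenged-only and as-received. The cost is one sentence and a denominator flag. The tables will then carry two safety denominators, and each must be labelled.
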